### 5.5 Risks and Privacy Concerns:

We do not foresee any significant risks for subjects/caregivers:

- Participants will continue to receive usual treatments including having their temperature monitored by their clinical team and caregivers according to standard care protocols.
- Participants are free to leave the study at any point without restriction.
- While we do not expect the iThermonitor to fail, the risk involved revolves around failure to appropriately notify subject/caregiver of a true fever episode or the generation of a false out-of-range temperature alert. Therefore, we will emphasize that subjects/caregivers should continue to monitor their temperature as recommended by their care providers. In the event of an out-of-range temperature alert, we will encourage subjects/caregivers to confirm the out-of-range temperature with their personal thermometers before notifying their care providers.
- Although subjects/caregivers are asked to complete questionnaires at the start and at the end of the study they will be instructed that they can choose not to answer any question(s) they do not wish to answer.
- The study team members responsible for completing chart reviews to gather the required information will be CITI certified and well-versed in HIPAA requirements. These team members will be trained and familiarized with the process of obtaining the required data points and will minimize viewing of any non-essential information.

Data security and privacy will be maintained through:

- Separation of participant names from all study data will be done through the use of unique identifiers. Only Study ID numbers will be used on the iThermonitor Application.
- The record review will be done by IRB approved study staff and will be focused only at collecting pre-specified information namely, temperature data while on hospitalization, type and stage of cancer and treatment regimens.
- Any information transferred via the internet will be done using 128 bit SSL encryption.
- Virus and password protected facilities within the Partners Healthcare network of computers will be provided for the research team.
- To safeguard confidentiality, access to all collected data will be limited to only the IRB approved study staff. Study subjects will be referred to by a unique study number and not by name.
- All communications via telephone or other media with subjects/caregivers will be stored in their study file.

- At the end of the study, all identifiable information will be destroyed and the study data will be maintained for at least two years after the completion of the study.
- Only de-identified outcomes data will be shared with study sponsors at the end of the study.
- Identifiable information will not be used or disclosed except as required by law, for authorized oversight of research, or for other research for which the use and disclosure would be permitted.

## 5.6 Description of Study Process:

Each subject/ caregiver dyad will participate in this pilot study for 2 weeks starting from the next day after the onset of chemotherapy. There are two study visits involved:

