## **5.0 Study Design and Materials**

5.1 Study Design: This study will be implemented as a pilot study to evaluate the use feasibility of the iThermonitor as a clinical decision support tool for the continuous temperature monitoring in pediatrics patients (on myelosuppressive therapies for acute leukemia and other childhood cancers at the MGH Cancer Center) and their caregivers over a 2-week study period upon the start of device use. This will ensure that 14 days of data is collected. Apart from the enrollment and closeout procedures that will be occur in the hospital settings, all other procedures will be performed at home. The iThermonitor will only be used by the patient-caregiver dyad at home for 14 days of data collection (starting from the next day post-chemotherapy) to monitor the patient's temperature. For hospitalized patients, their 14 days will start from the first day after hospital discharge.

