#### ***Registration Process for DF/HCC and DF/PCC Institutions***

The QACT registration staff is accessible on Monday through Friday, from 8:00 AM to 5:00 PM Eastern Standard Time.

The registration procedures are as follows:

- Obtain written informed consent from the participant prior to the performance of any protocol specific procedures or assessments.
- Complete the QACT protocol-specific eligibility checklist using the eligibility assessment documented in the participant's medical record and/or research chart. **To be eligible for registration to the protocol, the participant must meet all inclusion and exclusion criterion as described in the protocol and reflected on the eligibility checklist.**
- Fax the eligibility checklist(s) and all pages of the consent form(s) to the QACT at [contact]. For Phase I protocols, attach participant dose level assignment confirmation from the sponsor.
- The QACT Registrar will (a) review the eligibility checklist, (b) register the participant on the protocol, and (c) randomize the participant when applicable.
- An email confirmation of the registration and/or randomization will be sent to the Overall PI, study coordinator(s) from the Lead Site, treating investigator and registering person immediately following the registration and/or randomization.

5.63 During the study:

- If the study team does not receive data from the iThermonitor by the second day after study enrollment, study staff will follow-up (telephone call) with subjects to ensure that they are able to correctly set-up the device. We will encourage participants to continue to receive medical treatment and adhere to other management protocols as recommended by their physicians as usual. We will emphasize that the iThermonitor does not replace usual temperature monitoring protocols.
- Use the iThermonitor everyday to monitor the patient's temperature continuously until final study closeout.
- Complete the event monitoring log every day.
- In the event of a hospital admission during the study period, the hospitalized subject will stop using the device. If the subject has contributed less than 50% of data (i.e. used the device for less than 7 days) prior to hospitalization, they will be dropped from the study and another subject will be recruited to make up the enrollment

target. However, subjects who have contributed at least 50% of data prior to hospitalization will stop using the device but will be included in final analyses.

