#### 5.64 Close out visit:

- This visit will occur 2 weeks post-chemotherapy. If possible, subjects will schedule their final study visit at the enrollment visit. Study staff will also send an appointment reminder letter in the mail 3 days prior to the scheduled visit. They will also receive a reminder phone call to confirm the appointment a day before the final study visit. If participants would like, they can complete close-out surveys online via RedCap and return study devices during their next doctor visit or via a provided pre-paid FedEx envelope.

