### 6.1 Primary and secondary endpoints

6.1a Primary outcome measurement: use feasibility of the iThermonitor will be assessed by ability of the device to successfully capture, transmit and display the patient's body temperature data on the study iPad mini. To limit recall bias, subjects will be required to log (Appendix 5) the ability to view the temperature data on the iPad mini once a day for the entire duration of the study. The device will be deemed a feasible continuous temperature monitoring tool if at least 80% of study subjects are able to successfully use the iThermonitor to monitor their body temperature. A subject must be able to view temperature data on the provided iPad mini at least 80% of the time in the study to be considered successful. "Time in the study" here is defined as the number of days the subject spends in the study which is expected to be two weeks.

6.1b Secondary outcomes: secondary outcomes which will be assessed at the end of the study include:

- i. Usability, acceptability and satisfaction with the iThermonitor. This will be assessed by questionnaires specifically designed for this study. We will be assessing ease of use, acceptability, connection and use problems like the device falling off the skin, usefulness of out-of-range temperature alerts and adverse reactions. We will also assess to see if the device helps to build caregiver self-efficacy skills in caring for the patient.
- ii. Caregiver engagement with the iThermonitor. This will be assessed by time to first measurement and upload from the time of discharge and also by the frequency of logins to the iThermonitor app.
- iii. Caregiver anxiety will be assessed using the GAD-7 questionnaire.

6.2 Sample size and statistical power or precision associated with the sample size: The length of time required to accrue an adequate number of subjects to the study should be indicated.

We will be able to estimate a feasibility success rate of 80% to within a 95% confidence interval of +/- 16% with a sample size of 25 evaluable patients. This is in keeping with a

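### Sections 5.1, 5.6 and 5.64 disagree on when the 14 device days start and end, so an inpatient can pass or fail the primary criterion depending on the section followed, and one engagement measure has no time zero for clinic-enrolled patients.

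*Combined protocol and SAP*

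**What the plan says.** **Start of the 14 days.** Section 5.1 describes the study as running "over a 2-week study period upon the start of device use". It has device use "starting from the next day post-chemotherapy", with a branch for inpatients: "For hospitalized patients, their 14 days will start from the first day after hospital discharge". Section 5.6 instead has each dyad take part "for 2 weeks starting from the next day after the onset of chemotherapy" and mentions no inpatient branch.

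**End of the 14 days.** On close-out, section 5.64 states: "This visit will occur 2 weeks post-chemotherapy". Again there is no inpatient branch. The assessment table in 5.4 allows ±5 days around close-out. Section 5.63 has the device used daily until close-out.

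**Where the device may be used.** Section 4.1 bars use until the patient is home. Section 5.61 gives two enrollment routes: at a clinic visit for chemotherapy, or the day before discharge for hospitalized patients.

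**What depends on the window.** Sections 2.1 and 6.1a call a subject successful if temperature data can be viewed on at least 80% of the time in the study. That time is the number of days spent in the study, expected to be 14. Section 6.1b measures caregiver engagement partly by "time to first measurement and upload from the time of discharge".

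**The concern.** For an inpatient, the start in 5.1, the start in 5.6 and the close-out in 5.64 cannot all be met unless discharge falls on the chemotherapy day itself. Either device days are lost at the end, or days on which use was barred are counted at the beginning.

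This reaches the primary endpoint, because the per-subject criterion is a proportion of time in the study and the sections give different answers for when that time begins. Two analysts working from the same log could classify the same child differently, and the classification would reflect enrollment route and length of stay rather than how the device performed.

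The engagement measure has a related gap. Elsewhere the protocol uses discharge to mean leaving hospital, so a patient enrolled at a clinic visit has no stated time zero. An inpatient's clock starts at discharge although device use is scheduled for the following day.

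**Working it through.** **Inputs from the documents.** 14 device days (5.1); 80% per-subject criterion (2.1, 6.1a); close-out 2 weeks post-chemotherapy (5.64), ±5 days (5.4); home use only (4.1); use until close-out (5.63); 25 evaluable patients (6.2).

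**Assumption.** The documents give no length of stay. Let d be the days from chemotherapy to discharge, taken as 0 to 7.

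**The plan's own figures.** The half-width in 6.2 reproduces: 1.96 × √(0.8 × 0.2 / 25) = 0.157, which rounds to 16%. This point does not affect it. For a full 14 days the success criterion is 0.8 × 14 = 11.2, so 12 days.

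**Step 1: device days available before close-out.** With chemotherapy on day 0, discharge is day d, device day 1 is day d + 1, and close-out is day 14 + w, where w is −5, 0 or +5. Device days available = min(14, 14 + w − d).

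| d | nominal (w = 0) | late end (w = +5) | early end (w = −5) |
|---|---|---|---|
| 0 | 14 | 14 | 9 |
| 3 | 11 | 14 | 6 |
| 5 | 9 | 14 | 4 |
| 7 | 7 | 12 | 2 |

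**Step 2: effect on the success criterion.** Take an inpatient discharged 3 days after the onset of chemotherapy, with data viewed on every day at home.

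- Time in the study counted as in 5.6 (two weeks from the day after onset): days 1 to 3 count but use is barred, so the maximum is 11/14 = 78.6%. This is a failure. Because 5.6 fixes the period at two weeks, a late close-out does not change it.
- Counted from the post-discharge start in 5.1 for 14 days: 14/14, a success.
- Counted from the post-discharge start to the nominal close-out (one-day chemotherapy assumed): 11/11, a success on fewer days.

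On the 5.6 reading, discharge 2 days after onset still passes (12/14 = 85.7%). Any discharge 3 or more days after onset fails, however well the device works.

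**Step 3: onset against post-chemotherapy.** For a one-day infusion the two starts coincide. For a 5-day course (assumed), onset is 4 days earlier than the last chemotherapy day, so the two starts differ by 4 days.

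**Step 4: effect on the study result.** Each reclassified patient changes the success rate by 1/25 = 4 percentage points; two change it by 8, about half the planned half-width. The number of inpatients is not given, so a total shift cannot be computed.

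**Step 5: engagement zero.** For inpatients the origin is discharge and the scheduled start is the next day, so a wait is built in. For clinic-enrolled patients no origin is stated.

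**The case against.** The intent is fairly clear. Section 5.1 ties the period to the start of device use and says 14 days of data will be collected; the daily log in Appendix 5.2 has 14 rows; close-out surveys can be done online with the device returned later. The post-discharge start is a deliberate branch of one rule, needed because use is at home only, and should not be read as a third unrelated start. Staff who use the late end of the ±5 day window recover all 14 days for delays up to 5 days. Loss of days is therefore possible, not the planned result. All of this stands, but nothing directs staff to the late end for inpatients, and 5.6 and 5.64 still state a different rule.

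The denominator is also not fixed at 14: a shorter stay in the study shrinks it, so success remains attainable (8 of 9 days at d = 5 with nominal close-out). That is right if counting starts at device day 1. It does not help if counting starts as in 5.6.

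The engagement gap is minor: login frequency, the other engagement measure, is unaffected, and both are only summarized descriptively.

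Two stronger readings are tempting, and the documents do not support them. A reader might infer that late-discharged inpatients fall foul of the 7-day evaluability rule. Sections 5.63 and 6.6 apply that rule to subjects admitted during the study, on data contributed before that admission; it does not judge a late first discharge. A reader might also count the set-up call, triggered if no data arrive "by the second day after study enrollment", as another conflicting clock. It is an operational check. Inpatients enroll the day before discharge, so it falls on their device day 1; for a one-day clinic infusion it falls on device day 2.

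**Conclusion.** The point holds as an internal contradiction in operative text: 5.1, 5.6 and 5.64 do not define one observation window, and the inpatient exception appears only in 5.1. At the nominal close-out an inpatient loses d of 14 device days. The window can remove that loss for d up to 5 or deepen it, depending on which end is used.

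The more serious consequence is for the primary endpoint. On the 5.6 reading a discharge 3 or more days after onset makes success impossible, while the post-discharge reading leaves it attainable; each affected patient is worth 4 points of the success rate. The engagement measure's missing origin for clinic-enrolled patients is a real but smaller gap.

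These sizes rest on an assumed length of stay and, for the gap between the two chemotherapy anchors, an assumed course length. The documents do not show that days will be lost or how many patients would be affected.

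**What to change.** Reconcile 5.1, 5.6 and 5.64 to one scheduled device day 1 for each enrollment route. Which chemotherapy anchor applies is for the investigators to decide.

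- Define time in the study (2.1, 6.1a) as counted from that scheduled day.
- Count close-out (5.64 and the 5.4 table) from the same day, so that every dyad has 14 device days available before close-out. The early side of the ±5 day window has to meet this condition too, since it leaves only 9 days even at d = 0.
- Time first measurement and upload (6.1b) from the scheduled device day 1 for both routes. It must be the scheduled day: measured from actual first use, the time would be near zero by construction.

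The cost is wording in these sections, settled before the data are analyzed. No extra visits, patients or data items are needed.

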### 5.61 Enrollment visit:

This will take place during the clinic visit for chemotherapy or on the day before discharge for hospitalized patients.

- Enrollment into the study by signing the informed consent form. This will be done before performing any study procedures.
- Rescreening to confirm eligibility as described above. A screening checklist will be provided to guide the RA.
- Complete all enrollment surveys. Caregivers will be required to complete the GAD-7
- The research assistant will explain and demonstrate how to use the iThermonitor and also leave subjects with user manuals. (Appendices 1.4.)
- Subjects who wish to use their own smartphones, in addition to the provided study iPad minis, will be instructed to download the iThermonitor's app on the app store.
- Finally, study staff will emphasize that the iThermonitor is not a replacement for usual temperature monitoring protocols and will instruct participants to continue to receive medical care from their physicians as usual.

### 5.62 Registration Procedures

#### ***General Guidelines for DF/HCC and DF/PCC Institutions***

Institutions will register eligible participants with the DF/HCC Quality Assurance Office for Clinical Trials (QACT) central registration system.

An investigator will confirm eligibility criteria and a member of the study team will complete the QACT protocol-specific eligibility checklist.

#### ***Registration Process for DF/HCC and DF/PCC Institutions***

The QACT registration staff is accessible on Monday through Friday, from 8:00 AM to 5:00 PM Eastern Standard Time.

The registration procedures are as follows:

- Obtain written informed consent from the participant prior to the performance of any protocol specific procedures or assessments.
- Complete the QACT protocol-specific eligibility checklist using the eligibility assessment documented in the participant's medical record and/or research chart. **To be eligible for registration to the protocol, the participant must meet all inclusion and exclusion criterion as described in the protocol and reflected on the eligibility checklist.**
- Fax the eligibility checklist(s) and all pages of the consent form(s) to the QACT at [contact]. For Phase I protocols, attach participant dose level assignment confirmation from the sponsor.
- The QACT Registrar will (a) review the eligibility checklist, (b) register the participant on the protocol, and (c) randomize the participant when applicable.
- An email confirmation of the registration and/or randomization will be sent to the Overall PI, study coordinator(s) from the Lead Site, treating investigator and registering person immediately following the registration and/or randomization.

5.63 During the study:

- If the study team does not receive data from the iThermonitor by the second day after study enrollment, study staff will follow-up (telephone call) with subjects to ensure that they are able to correctly set-up the device. We will encourage participants to continue to receive medical treatment and adhere to other management protocols as recommended by their physicians as usual. We will emphasize that the iThermonitor does not replace usual temperature monitoring protocols.
- Use the iThermonitor everyday to monitor the patient's temperature continuously until final study closeout.
- Complete the event monitoring log every day.
- In the event of a hospital admission during the study period, the hospitalized subject will stop using the device. If the subject has contributed less than 50% of data (i.e. used the device for less than 7 days) prior to hospitalization, they will be dropped from the study and another subject will be recruited to make up the enrollment

target. However, subjects who have contributed at least 50% of data prior to hospitalization will stop using the device but will be included in final analyses.

#### 5.64 Close out visit:

- This visit will occur 2 weeks post-chemotherapy. If possible, subjects will schedule their final study visit at the enrollment visit. Study staff will also send an appointment reminder letter in the mail 3 days prior to the scheduled visit. They will also receive a reminder phone call to confirm the appointment a day before the final study visit. If participants would like, they can complete close-out surveys online via RedCap and return study devices during their next doctor visit or via a provided pre-paid FedEx envelope.

#### Participants will:

- Complete all close-out surveys
- Return the provided iPad mini devices.
- Be instructed to continue their medical care as usual.

#### 5.65 Instrument administration

All study questionnaires will be administered by research assistants.

#### 5.66 Intervention administration

At enrollment, study staff will demonstrate how the device works to subjects. They will also be available to answer questions or help subjects troubleshoot their devices. Subjects will receive user manuals to guide them for subsequent set-up and use. (Appendices 1.4,) They will be encouraged to use the iThermonitor to monitor the patient's body temperature continuously for the 2-weeks study period.

#### 5.67 Special Concerns

One special concern in this study is that the intervention may increase the sensitivity of detection of fever which may prompt caregivers to alerts care providers and hence increase the reporting of fever. We will instruct caregivers to confirm out-of-range temperature alerts with standard thermometers before notifying their care providers. We will emphasize that this intervention does not replace their usual care protocols.

#### 5.68 Remuneration

Each patient-caregiver dyad will receive a Partners-issued check of \$100 after completing the final study visit and returning the study iPad mini. The check will be mailed at the end of the study. No additional remuneration or reimbursement will be provided.

#### 5.7 Adverse Reactions and their Management:

There is minimal chance for adverse effects directly from this study. However, because the iThermonitor is attached to the skin a hydrogel dressing patch, we cannot rule out the possibility of a skin reaction to the adhesive surface of the device. After discharge from the hospital, we will instruct caregivers to continue monitoring patients as recommended by their care providers. While we do not expect the iThermonitor to fail, we will emphasize that caregivers are to continue all standard protocols care for each patient.

